Description of change		
 
1. Infusion time for dose groups 10 mg/kg b.w. multiple doses and 20 mg/kg b.w. single dose was prolonged to 60 minutes
 
2. Update of reconstitution instructions:             
 
a. 1 mL syringe was added in 3 mg dose group
 
b. Material information for consumables was added
 
c. Infusion time was updated
 
 
 
3. Update of stability of reconstituted/diluted solution / In-Use-Stability
 
4. Update of study flow chart:             
 
a. Additional visits for follow-up observation (until 20 weeks after last dosing) with respective time-windows were included for all dose groups
 
b. Infusion time for dose group 10 mg/kg b.w. multiple doses and 20 mg/kg b.w. single dose was extended to 60 minutes.
 
c. Body weight measurement was included at visit 2/day -2
 
d. Time window for procedures performed before drug administration was adapted
 
 
 
5. Correction of inconsistencies and typing errors throughout the document
 
6. Update regarding blood sampling
 
7. Update to align with final data after database lock in July 2016
 

Rationale for change		
 
1. Updated In-Use Stability Study with date from 24 August 2016
 
2. Updated In-Use Stability Study with date from 24 August 2016
 
3. Updated In-Use Stability Study with date from 24 August 2016
 
4.             
 
a. PK results from 1368.1 trial suggest a half-life of BI 655130 of about 4 weeks for doses tested in the study. The evaluation is ongoing. However as precautionary measure we have
 
 
 

Number of global amendment		1
		
extended the observation period to Day 176 to cover at least 5 half-lives
 

b. Updated In-Use Stability Study with date from 24 August 2016

c. Correction to align with eCRF

d. For logistical reasons

 

5. A few inconsistencies and typing errors were corrected

6. Left over blood samples will be discarded after 5 years instead of 3 years

7. Data were aligned with final data after database lock

Number of global amendment	2
Date of CTP revision	05 Dec 2016
EudraCT number	2016-001235-12

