2. LIST OF ABBREVIATIONS

Term	Definition / description
ADPC	Proper name of the analysis dataset containing PK concentrations per time-point or per time-interval
ADPP	Proper name of the analysis dataset containing calculated PK parameters
ADS	Analysis dataset
AE	Adverse event
AESI	Adverse event of special interest
AIC	Akaike's information criterion
ALT	Alanine aminotransferase
AST	Aspartate aminotransferase
AUC _{0-∞}	Area under the concentration-time curve of the analyte in plasma over the time interval from 0 extrapolated to infinity
AUC _{τ,ss}	Area under the concentration-time curve of the analyte in plasma at steady state over a uniform dosing interval τ
AUC _{τ,1}	Area under the concentration-time curve of the analyte in plasma over a uniform dosing interval τ after administration of the first dose
AUEC _{above}	Area above the biomarker effect vs. time curve above the baseline during the treatment interval
AUEC _{below}	Area under the biomarker effect vs. time curve below the baseline during the treatment interval
AUEC _{diff}	Difference between AUEC _{below} and AUEC _{above}
BI	Boehringer Ingelheim
BLQ	Below the lower limit of quantification
BMI	Body mass index
BMS	Biomarker set
CARE	Clinical data analysis and reporting environment
CI	Confidence interval
C _{max}	Maximum measured concentration of the analyte in plasma after administration of the first dose
C _{max,ss}	Maximum measured concentration of the analyte in plasma at steady state
CRF	Case report form

Term	Definition / description
CTP	Clinical trial protocol
CTR	Clinical trial report
CV	Arithmetic coefficient of variation
DBLM	Database lock meeting
E_{base}	Baseline effect of biomarker
ECG	Electrocardiogram
ECGPCS	Electrocardiogram plasma concentration set
eCRF	Electronic case report form
EMA	European Medicines Agency
E_{max}	Maximum effect of biomarker
EudraCT	European union drug regulating authorities clinical trials
gCV	Geometric coefficient of variation
gMean	Geometric mean
HR	Heart rate
ICH	International Council for Harmonisation of Technical Requirements for Pharmaceuticals for Human Use
IPV	Important protocol violation
MD	Multiple dose
MedDRA	Medical Dictionary for Regulatory Activities
NOA	Not analysed
NOP	No peak detectable
NOR	No valid result
NOS	No sample available
on-trt	on-treatment
PD	Pharmacodynamic(s)
PK	Pharmacokinetic(s)
PKS	Pharmacokinetic parameter analysis set
PR interval	ECG interval from the onset of P wave to the beginning of the QRS
PV	Protocol violation

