6.7 BASELINE, TIME WINDOWS AND CALCULATED VISITS

6.7.1 Time points and baseline for analysis of 12-lead ECG

There will be a centralised evaluation of all 12-lead ECG recordings at the time points specified in Table 6.7: 1 below:

Table 6.7.1: 1 Time schedule of 12-lead ECG recordings with centralised evaluation

Visit	Day	Planned time [hh:mm] (relative to respective drug administration)	Comment ²	Study phase
2	1, 8 ¹ , 15 ¹ and 22 ¹	-02:00		Baseline/on-trt ³
		00:30	only for BI 3 mg/kg MD, 6 mg/kg MD and BI 20 mg/kg SD	On-treatment
		01:00	only for BI 10 mg/kg MD and BI 20 mg/kg SD	
		01:30	only for BI 20 mg/kg MD and BI 20 mg/kg SD	
		02:00		
		03:00	only for BI 20 mg/kg SD	
		04:00	only for BI 20 mg/kg SD	
		06:00		
		08:00	only for BI 20 mg/kg SD	
		12:00		
2, 9 ¹ , 16 ¹ and 23 ¹		24:00		
		32:00	only for BI 20 mg/kg SD	
3, 10 ¹ , 17 ¹ and 24 ¹		48:00		

¹ These days are only applicable to dose groups with multiple dosing

² If no comment is given, time point is applicable to all dose groups in this trial

³ ECG recording at relative time -2:00 h prior to next dosing is considered to be baseline on Day 1 and to be on-treatment on other days

Triple ECGs (3 single ECGs recorded within 180 sec) will be recorded on all time points with centralised ECG evaluation (as listed in the table above). On all other time points, single ECGs will be recorded.

The value of an ECG variable at each of the time points with triple ECG is defined as the arithmetic mean of the 3 single ECG measurements. In particular, the baseline value of an ECG variable is defined as the mean of the triple ECG measurements prior to first drug administration.

For the exposure-response analysis, ECG measurements and corresponding plasma concentrations building pairs using the same planned time points will be used (e.g., QTcN change from baseline and plasma concentration for planned time 0:30 will build one pair.) Whether a time deviation between a PK sample and the corresponding ECG recording is too big and the respective pair has to be excluded, or whether a value has to be matched to another time point, will be decided no later than at the RPM/DBLM.

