6.7.4 Pooled time points for comparison of endpoints at end of infusion

The duration of infusion varies between dose groups, as shown in the table below.

Table 6.7.4: 1 Duration of infusion

Dose group	Duration of infusion
BI 3 mg/kg MD and matching placebo	30 min
BI 6 mg/kg MD and matching placebo	30 min
BI 10 mg/kg MD and matching placebo	60 min
BI 20 mg/kg MD and matching placebo	90 min
BI 20 mg/kg SD and matching placebo	60 min

Therefore, the planned time of measurements taken at the end of infusion also varies between dose groups (e.g., 0:30 h, 1:00 h or 1:30 h after infusion on Day 1). In order to allow comparison between dose groups at the end of infusion, the following time points will be defined for use in statistical analysis of vital signs, body temperature, ECG results and biomarkers. They will be created by pooling the time points at the end of infusion of all dose groups.

Table 6.7.4: 2 Time points for statistical analysis of vital signs, body temperature, ECG and biomarkers

Visit	Day	Time point label	Planned time [hh:mm] (relative to first drug administration)				
			BI 3 mg/kg MD	BI 6 mg/kg MD	BI 10 mg/kg MD	BI 20 mg/kg MD	BI 20 mg/kg SD
2	1	Day 1, end of inf.	0:30	0:30	1:00	1:30	1:00
2	8	Day 8, end of inf.	168:30	168:30	169:00	169:30	NA
2	15	Day 15, end of inf.	336:30	336:30	337:00	337:30	NA
2	22	Day 22, end of inf.	504:30	504:30	505:00	505:30	NA

NA = Not applicable.

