If there is no non-linearity or delayed effect seen, the relationship between BI 655130 plasma concentrations and QTcN changes from baseline will be investigated in an exploratory manner using a random coefficient model approach to estimate the QTcN change from baseline and its 90% confidence interval at the geometric mean of the C_{max} for each dose (multiple dose groups as well as single dose group). Additionally, the estimated slope with its 90% confidence interval will be provided. The used random coefficient model is based on Garnett et al. 2016 [R17-0553] ([10](#)):

```
PROC MIXED DATA=myDATA METHOD=REML;
CLASS subject active(ref=FIRST) time;
MODEL ECGep = conc active time / NOINT CL ALPHA=0.1 ALPHAP=0.1 DDFM=KR
    OUTPREDM=pred;
RANDOM INT conc / TYPE=UN SUBJECT=subject;
ESTIMATE 'Pred. value at conc. xx.xx' conc xx.xx active 1 -1 / CL
    ALPHA=0.1;
ESTIMATE 'Slope estimate' conc 1 / CL ALPHA=0.1;
RUN;
```

Here "ECGep" is the QTcN change from baseline, "active" is a dummy 0/1 variable indicating the active treatment (1=active, 0=placebo), "conc" is the corresponding plasma concentration value of the drug, and "xx.xx" is the given concentration value (i.e. the value of the geometric mean C_{max} of a given dose group). The class variable "time" is the time relative to the most recent infusion; here, measurements at time points at the end of infusion will not enter the model with the planned time, but only by means of the time points defined in [Table 6.7: 3](#). The "TYPE=UN" option causes the two specified random coefficients to have a bivariate normal distribution. In case of convergence problems see [Section 9.2](#) for possible improvements (option "TYPE=FA0(2)" may also be used as a potential solution, it requests a G matrix estimate that is constrained to be nonnegative definite). If the note "estimated G matrix is not positive definite" occurs in the SAS log file, the random slope "conc" might be removed from the "RANDOM" statement. When the plasma concentrations are not normally distributed, the exposure-response model can be applied to $\log(\text{conc})$ instead of the raw concentration.

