For visualization, the BI 655130 plasma concentration against the response will be plotted as well as the (fixed effect) regression line, its 90% confidence interval and the geometric mean of C_{max} for each dose. For each subject and each time point, subtract the mean value of all individual observed ΔQTc values from the placebo group for this time point from the individual observed ΔQTc value for this subject and time point. This results in estimates for "individual $\Delta\Delta QTc$ " values. These estimates should only be used for plotting purposes.

All of the above described graphical and statistical analyses will be also performed for QTcF, HR and QT in place of QTcN.

Categorical Endpoints

For the categorical endpoints, frequency tables will be provided.

For subjects with notable findings, the individual time courses of QTcN, QTcF, QT, HR, PR, and QRS of these subjects will be presented in figures.

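### The exploratory concentration-QTc model has no dosing-day term, so a drift shared with placebo can load on the concentration slope; its log form has no rule for the placebo zeros

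*SAP*

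**What the plan says.** The model in SAP 7.8.4 is "MODEL ECGep = conc active time / NOINT CL ALPHA=0.1 ALPHAP=0.1 DDFM=KR", with a random intercept and a random concentration slope by subject. The class variable for time "is the time relative to the most recent infusion". End-of-infusion records are an exception: they enter "but only by means of the time points defined in" Table 6.7: 3. The SAP has no table of that number. Table 6.7.4: 2 is the likely target, and its labels name the day, for example "Day 8, end of inf".

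The response is measured from a single reference: "the baseline value of an ECG variable is defined as the mean of the triple ECG measurements prior to first drug administration" (SAP 6.7.1). Placebo subjects enter at concentration zero (SAP 6.3 and 7.8.4). The planned outputs are the slope with its 90% interval and the predicted effect at the geometric mean Cmax of each dose. They are repeated for QTcF, QT and HR.

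The SAP abbreviation list defines Cmax as "Maximum measured concentration of the analyte in plasma after administration of the first dose". For plotting only, each subject's change has subtracted from it the mean of "values from the placebo group for this time point from the individual observed" change. The model may also be fitted to log concentration when concentrations are not normally distributed.

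Dosing in the multiple-dose part is on Days 1, 8, 15 and 22 (Protocol 6.2.2). The rationale for amendment 1 (Protocol section 11) says "PK results from 1368.1 trial suggest a half-life of BI 655130 of about 4 weeks".

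**The concern.** The 12 h, 24 h and pre-dose records of different weeks share one time level each. At most the end-of-infusion records have a level per day. Because baseline is taken once, any drift over Days 1-22 stays in the response. Concentration is then the main fixed effect that follows the weeks, and it does so in active subjects only. A drift that both arms share and that resembles accumulation is partly assigned to concentration, and the active indicator shifts the opposite way. The placebo data could separate drift from drug, but the model gives them no term through which to do it. An upward drift can create a slope; a downward one can hide a real slope.

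If the placebo mean used for plotting is taken by nominal visit, the plotted points are corrected for drift by day and the fitted line drawn through them is not.

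The log option has a separate fault. Normality of a covariate is not a regression assumption, so the trigger is misplaced. Placebo concentration is zero by rule and log(0) is undefined. Run as written, the model would drop all 10 placebo subjects (2 in each of 5 groups), and the active-versus-placebo contrast in the ESTIMATE statement could not be estimated.

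**Working it through.** The documents give no figure for this model, so there is none to reproduce. The check asks what the model returns when the true drug effect is zero.

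**Inputs from the documents.** Four multiple-dose groups and one single-dose group, each 6 active and 2 placebo. Matched PK-ECG records in the multiple-dose part: end of infusion, 12 h and 24 h on Days 1, 8, 15 and 22, and pre-dose on Days 8, 15 and 22. Single dose: end of infusion, 2, 3, 4, 8, 12, 24 and 48 h. Half-life 28 days.

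**Assumptions not in the documents.** Shared linear drift of 2 or 5 ms from Day 1 to Day 22; between-subject SD 5 ms; residual SD 7 ms; a fast distribution phase of 0, 30 or 60% with half-life 2 days.

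**Accumulation.** With one-compartment decay, the fourth peak relative to the first is 1 + 2^(-7/28) + 2^(-14/28) + 2^(-21/28) = 1 + 0.841 + 0.707 + 0.595 = 3.14.

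**Expected bias by generalised least squares.** Ranges run over the three fast-phase settings. Millisecond rows are for +5 ms drift; -5 ms reverses the signs.

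| Quantity | All times pooled over days | End of infusion by day | Day term added |
|---|---|---|---|
| Slope bias / SE, 5 ms drift (fast phase 0, 30, 60%) | 3.5, 3.3, 2.7 | 2.7, 2.5, 2.0 | 0 |
| 90% slope CI excludes 0, 2 ms drift | 29-41% | 21-29% | 10% |
| 90% slope CI excludes 0, 5 ms drift | 86-97% | 64-85% | 10% |
| Bias at first-dose Cmax, 20 mg/kg (ms) | +0.1 to +1.3 | +0.1 to +1.0 | 0 |
| Bias at first-dose Cmax, 3 mg/kg (ms) | -2.0 to -2.2 | -1.5 to -1.7 | 0 |
| Bias at fourth-dose Cmax, 20 mg/kg (ms) | +4.8 to +5.7 | +3.7 to +4.6 | 0 |

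The exclusion rates follow from b = bias / SE as Φ(b - 1.645) + Φ(-b - 1.645). With end-of-infusion levels by day and no fast phase, b = 2.67 at 5 ms gives Φ(1.025) = 0.85. At 2 ms, b = 0.4 × 2.67 = 1.07 gives Φ(-0.58) + Φ(-2.71) ≈ 0.29.

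**How slope and active term offset each other.** Take residual SD 6 ms, no fast phase, 20% between-subject CV in exposure, and concentration in units of that produced by 1 mg/kg. With end-of-infusion levels by day, a 5 ms drift gives a slope of 0.1032 and an active term of -2.07 ms.

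- Fourth-dose peak at 20 mg/kg (mean 64.2 units): 0.1032 × 64.2 - 2.07 ≈ +4.6 ms.
- First-dose peak at 20 mg/kg (20.4 units): 0.1032 × 20.4 - 2.07 ≈ 0 ms.
- First-dose peak at 3 mg/kg (20.4 × 3/20 = 3.06 units): 0.1032 × 3.06 - 2.07 ≈ -1.8 ms.

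**Simulation under those same settings** (200 trials per drift size, REML, random intercept; slope CI excludes 0, pooled / end of infusion by day): no drift 11% / 13.5%; 2 ms 42% / 30.5%; 5 ms 99.5% / 91.5%. With a day term it is 10.5-12.5% throughout. Under the table's assumptions with random concentration slopes (SD 0.5 ms per 100 µg/mL, 100 replicates per case), 5 ms gives 84-93% / 61-83%, and 10-13% with a day term.

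**Sensitivity.** Over between-subject SD 3-8 and residual SD 5-10 ms, bias / SE at 5 ms is 1.4-5.3 pooled and 1.0-4.1 with end of infusion by day. The shape of the drift matters. A 5 ms step after Day 1 gives a slope of 0.084 against 0.103 for the linear drift (end of infusion by day, residual SD 6 ms). A 5 ms shift on Days 8 and 15 only moves the slope by just 0.2-0.3 SE.

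**The case against.** The strongest reply is that nothing in the documents points to a drift, and without one the slope is unbiased. That stands: the rates above depend on chosen drift sizes and SDs, and they move when those change.

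Some sources of drift are also already limited. Central ECG reading is blinded to date and time, in random sequence, by one technician per subject (Protocol 5.2.4.1). Recordings are supine, after rest and in triplicate, and food and methylxanthines are restricted. These steps address reader and procedural drift. They do not exclude physiological drift.

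The table reference is probably just old numbering. SAP section 6.7 has three tables, the third is Table 6.7.4: 2, and the SAP uses the same old style for its ECG time table. The end-of-infusion-by-day figures are therefore the better guide. They still leave most of the slope bias: 0.1032 / 0.1280 = 81% in the residual SD 6 ms case.

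At the listed first-dose Cmax, the bias at 20 mg/kg is at most about 1 ms on that reading. This also stands; the large values are at fourth-dose Cmax, which SAP 7.8.4 does not name. But the slope and its interval are planned outputs in their own right, and the 3 mg/kg prediction is off by more than 1 ms in the other direction.

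Finally, the analysis is exploratory and the log form optional. Descriptive profiles by treatment would show a shared drift, and the categorical outputs do not use this model. All of this limits the consequence without repairing the model.

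**Conclusion.** Both parts hold. As specified, the model cannot separate concentration from a drift that placebo shares and that tracks accumulation. If such a drift reached 5 ms by Day 22, a false non-zero slope would be the usual result on either reading of the table reference. At 2 ms the error rate would be two to four times nominal. The bias is nil without drift, small for drift unrelated to accumulation, and nearly cancels at first-dose 20 mg/kg Cmax. Drift size, SDs and the fast phase are assumptions, so the direction and mechanism are firmer than the percentages.

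The log option needs no such assumption: it cannot be run as written with placebo retained, as SAP 6.3 and 7.8.4 require. The point is worth correcting because the remedy is cheap. It does not affect the primary endpoint or the descriptive ECG analyses.

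**What to change.** 1. Add dosing day as a class effect for all records: `CLASS subject active(ref=FIRST) time day;` and `MODEL ECGep = conc active time day`, with the existing options. Code day as 1, 8, 15 or 22 by planned visit; pre-dose records take the day of that visit, and the single-dose group takes 1. Nominal day-by-time levels would serve equally well. The ESTIMATE statements are unchanged for the linear form.
2. Correct the reference to Table 6.7.4: 2, and state whether predictions use first-dose or fourth-dose Cmax.
3. Drop the normality trigger. Choose between linear and log concentration from residual plots, or by likelihood criteria under ML rather than REML.
4. If log is used, set the log term to 0 for placebo, keep the active indicator, and put the log of the chosen concentration in the ESTIMATE statement. Active BLQ records are already excluded, so no other zeros arise.

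The cost is SAP wording and code, plus some precision. Under the main assumptions the slope SE rises 14-28% against pooled levels and 10-21% against end of infusion by day. With residual SD 6 ms it rises from 0.0311 to 0.0400, or 29%, against pooled levels. The SE at fourth-dose 20 mg/kg Cmax rises 6-12% (5-9% against end of infusion by day), and at first-dose 20 mg/kg Cmax by less than 1%. The correction rests on the 8 multiple-dose placebo subjects and removes only drift common to the dose groups.

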6.3 SUBJECT SETS ANALYSED

The following subject sets will be defined for statistical analysis:

- Treated set (TS):
This subject set includes all subjects who received study drug.
- Pharmacokinetic parameter set (PKS):
This subject set includes all subjects of the TS who provide at least one observation for at least one secondary PK endpoint without important PVs with respect to the statistical evaluation of PK endpoints, as defined in Section 7.3.2 of the CTP.

[REDACTED]

All ECG analyses are performed on the TS, except for the exposure-response analyses, which are performed on the ECGPCS defined below.

- ECG PC set (ECGPCS):
This subject set includes all subjects from the TS who provide at least one pair of a valid drug plasma concentration and a corresponding (i.e. time-matched) ECG endpoint to be used in the exposure-response analysis. For placebo subjects, the plasma concentration is set to 0 and hence always valid. For subjects treated with BI 655130, the decision about concentration value validity needs to be assessed within the Clinical Pharmacology group. The decision whether a time deviation between PK blood sampling and ECG recording is acceptable (and thus whether the pair of values will be used) is to be made no later than at the RPM before data base lock.

The discussion of all exceptional cases and problems and the decisions on the allocation of subjects to analysis sets will be made at latest at the RPM/DBLM.

Table 6.3: 1 Subject sets analysed

Class of endpoint	Subject set			
	TS	PKS	BMS	ECGPCS
Disposition	X			
Exposure	X			
IPVs	X			
Demographic/baseline endpoints	X			
Primary endpoint	X			
ECG endpoints and plasma concentrations used in exposure-response analysis				X
ECG endpoints in other analyses	X			
Other safety parameters	X			
Secondary PK endpoints		X		
Further PK endpoints		X		
Biomarkers			X	

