7.8.4 ECG

12-lead ECG

Abnormal findings will be reported as baseline conditions (at screening) or as AEs (during the trial) if judged clinically relevant by the investigator.

All evaluation of ECG data except of exposure response analysis will be based on the TS. The exposure-response analysis will then be done on the ECGPCS.

Listing of individual data

For all quantitative endpoints, listings of individual data will be shown in Appendix 16.2. Occurrences of notable findings (as defined in [Section 5.3.2](#)) will be flagged.

For all subjects with any notable finding in quantitative ECG recordings, a separate listing will be created as end-of-text display (based on the same display template as in Appendix 16.2), and the corresponding time profiles will be shown.

Comments regarding the ECGs will be listed.

Descriptive analysis

Descriptive statistics (N, mean, SD, min, median, max) will be provided for the changes from baseline over time in all quantitative ECG variables, and time profiles of mean and SD for the changes from baseline on treatment will be displayed graphically by treatment.

Plasma concentrations and relationship to QTcN, QTcF, QT interval and HR change from baseline

For the following analyses, all time points with ECG recordings with centralised evaluation and corresponding plasma concentrations will be included.

The changes from baseline in QTcN (Δ QTcN) will be investigated as response variable. The placebo subjects will be included in the analysis, with zero plasma concentrations. Time points with plasma concentrations "BLQ" in subjects in active dose groups will be ignored in this analysis.

As a first step, it will be investigated if there is a potential delayed or accelerated (e.g. metabolites) effects of the drug on QTcN. A general visual impression of the PK-QT relationship is provided by overlaying time profiles of plasma concentrations and QTcN changes from baseline (Δ QTcN). All figures will be generated for each subject (presented in Appendix 16.1.9.2 of the CTR), as well as for means per active treatment (presented in Section 15.3 of the CTR).

In case of non-linearity or if there is evidence for a delayed effect, further models will be explored that better characterise the PK/ECG relationship (effect compartment, non-linear model etc.).

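### The SAP lets the concentration-QTc model move to log(conc) when concentrations are not normal, a condition that has no bearing on the model and will practically always be met

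*SAP*

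**What the plan says.** SAP 7.8.4 (ECG) sets out a sequence. Overlaid time profiles of concentration and QTcN change come first. Then: "In case of non-linearity or if there is evidence for a delayed effect, further models will be explored". The random coefficient model belongs to the other branch: "If there is no non-linearity or delayed effect seen, the relationship between BI 655130 plasma concentrations and QTcN changes from baseline will be investigated". Its fixed part is written on the raw scale, "MODEL ECGep = conc active time / NOINT CL ALPHA=0.1", with a random intercept and a random slope on concentration. The outputs are the slope and the predicted effect at the geometric mean C_max of each dose, both with 90% confidence intervals.

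On placebo, 7.8.4 states: "The placebo subjects will be included in the analysis, with zero plasma concentrations". SAP 6.3 agrees: "For placebo subjects, the plasma concentration is set to 0 and hence always valid".

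After the convergence advice, one further sentence gives the option at issue: "When the plasma concentrations are not normally distributed, the exposure-response model can be applied to" log(conc). It names no normality test, no criterion of fit and no rule for zeros, and it does not say which version is the reported one. Section 7.8.4 repeats the whole analysis for QTcF, HR and QT.

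**The concern.** A linear mixed model assumes normal residuals and random effects. It assumes nothing about the distribution of a covariate. Whether concentrations are normal therefore cannot show whether QTc changes with concentration or with its logarithm. A condition that is irrelevant and almost certain to be met works in practice as an open choice of scale. The protocol (4.1.5.1) has the sponsor's statistician and pharmacokineticist unblinded, so that choice could be made with the data in view.

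The position of the sentence adds to the difficulty. Departures from linearity have their own route in 7.8.4, yet the option to bend the relation sits in the branch meant for data without such a departure. At stake are the slope and the predictions at each dose's C_max, which are what this analysis delivers.

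**Working it through.** The plan gives no figure on this point to reproduce. Its ALPHA=0.1 agrees with the 90% intervals.

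**Inputs from the documents.** Four doses of 3, 6, 10 or 20 mg/kg, or one dose of 20 mg/kg (SAP 6.1). Six active and two placebo subjects in each of five groups (protocol 3.1), so 30 active and 10 placebo. Half-life about 4 weeks (protocol section 11, rationale for Amendment 1). Matched PK and ECG times from the flow charts and SAP 6.7.1.

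**Assumptions not in the documents.** Variability in PK and QTc, and a truly linear effect of 10 ms at the accumulated 20 mg/kg level. All fits used a random intercept without the SAP's random slope.

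**1. Will the condition hold?**
- Dose range: 20/3 = 6.7-fold.
- Accumulation by the fourth dose at a 28-day half-life: 1 + 0.841 + 0.707 + 0.595 = 3.14.
- Spread of typical peaks: 6.67 × 3.14 = 20.9-fold.
- Pairs: 32 multiple-dose subjects × 15, plus 8 single-dose subjects × 8, gives 544. A quarter of the subjects are on placebo, so 136 pairs (25%) are exact zeros.

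In simulated trials (between-subject CV 15 to 50%, mono- or bi-exponential decline), a Shapiro-Wilk test at 5% rejected normality in every trial, with the zeros and among active subjects alone. Half-lives of 14, 28 and 42 days gave the same result among active subjects. Taking logs did not cure it: logged active concentrations were still rejected in 69 to 100% of trials.

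**2. Can the log model be fitted as written?** log(0) is undefined. Without a rule, all 136 placebo pairs drop out and the contrast in "ESTIMATE 'Pred. value at conc. xx.xx' conc xx.xx active 1 -1" cannot be estimated.

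**3. What does the log scale do to a linear truth?**

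Set A: one compartment, half-life 28 days, between-subject log-SD 0.25, QTc between-subject and residual SD 6 ms each. True values: 10 ms at the fourth-dose 20 mg/kg peak, 10/3.14 = 3.2 ms at the first-dose 20 mg/kg peak, and 3.2 × 3/20 = 0.5 ms at the first-dose 3 mg/kg peak. Results come from two runs of 40 and 30 trials. The 30-trial run set placebo to 0 on the log scale; the zero rule is not specified for the other. Monte Carlo SE in the 30-trial run was about 0.4 to 0.5 ms.

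Set B: log(conc+1), PK CV 20%, subject SD 3 ms, residual SD 5 ms, mono- and bi-exponential decline, 45 trials each, Monte Carlo SE of the raw-scale estimates about 0.2 to 0.3 ms. C_max is the highest value in the profile, so it is accumulated for the multiple-dose groups.

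| Set, point | True (ms) | Raw conc | Log scale |
|---|---|---|---|
| A, 3 mg/kg first dose | 0.5 | 0.5 (40-trial run) | -1.3, -1.6 |
| A, 20 mg/kg first dose | 3.2 | 3.2 (40-trial run) | 3.9, 3.7 |
| A, 20 mg/kg fourth dose | 10.0 | 9.7, 9.6 | 7.0, 7.0 |
| B, 3 mg/kg accumulated | 1.54, 1.54 | 1.53, 1.76 | 1.84, 2.00 |
| B, 6 mg/kg accumulated | 3.09, 3.09 | 3.05, 3.29 | 3.75, 4.00 |
| B, 20 mg/kg single dose | 3.38, 4.65 | 3.34, 4.80 | 4.01, 5.22 |
| B, 20 mg/kg accumulated | 10.0, 10.0 | 9.81, 10.04 | 7.12, 7.56 |

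- Accumulated 20 mg/kg: (10 - 7.56)/10 = 24% to (10 - 7.0)/10 = 30% too low.
- First-dose 20 mg/kg (A): 3.7 - 3.2 = 0.5 to 3.9 - 3.2 = 0.7 ms too high.
- First-dose 3 mg/kg (A): -1.3 - 0.5 = -1.8 to -1.6 - 0.5 = -2.1 ms, so too low. At the accumulated 3 mg/kg peak this does not carry over; set B was slightly high there.
- Zeros dropped, 20 minus 3 mg/kg at accumulated peaks: 4.94 to 5.10 ms against a true 8.46 ms, about 40% too small.

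**4. Range over effect size.** The bias is proportional to the true slope. At the accumulated 20 mg/kg level, 24 to 30% of a 5, 10 or 20 ms effect is 1.2 to 1.5, 2.4 to 3.0 or 4.8 to 6.0 ms. With no effect it is zero.

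**The case against.** The strongest reply is that the consequence is small. The wording is permissive, the written code uses raw concentration, and the analysis is exploratory. Section 7.8.4 also asks for a plot of concentration against response with the fitted line, where gross misfit would show. With 30 active and 10 placebo subjects and set A's variances, the 90% interval has a half-width of about 3.7 to 4.1 ms at the first-dose C_max values. Even the error of about 3 ms at the accumulated level lies within a half-width of about 4.1 ms. All of this stands and limits the weight of the point. None of it makes the condition a valid reason to change scale.

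Three stronger readings are tempting, and the documents do not support them.

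- A reader might infer that the reported top-dose effect would be understated by 30%. The SAP's abbreviation list defines C_max as the maximum after the first dose and C_max,ss as a separate quantity. If predictions are made at the first-dose C_max, the error at 20 mg/kg is a small overstatement. The shortfall appears in the output only if the accumulated level is used.
- A reader might infer that the log scale contradicts a finding of linearity. The first step in 7.8.4 offers only a visual impression from overlaid time profiles. It contains no residual plot or AIC comparison, so linearity will not have been formally established.
- A reader might infer a threat to safety decisions. The primary endpoint is drug-related AEs, the QT criterion for stopping escalation (protocol 3.3.4.2) uses individual values, and the categorical QTc tables do not depend on this model.

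**Conclusion.** The point holds as a fault in the rule. The distribution of the covariate is no ground for changing the model scale, the condition will practically always be satisfied, and the log version cannot be run as written with placebo at zero. If the relation is linear, the log scale distorts the slope and predictions. They are too low at the first-dose C_max of 3 mg/kg, slightly too high at the first-dose C_max of 20 mg/kg, and about 24 to 30% too low at accumulated 20 mg/kg levels.

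The percentages rest on an assumed linear 10 ms effect, assumed PK and variance values, a chosen treatment of zeros and fits without the random slope. The 0.5 to 0.7 ms overstatement is close to Monte Carlo error in the 30-trial run, though set B's single-dose group shows the same direction. The reach is limited to the exploratory exposure-response analyses of QTcN, QTcF, QT and HR. It should be corrected, but no primary result or escalation rule depends on it.

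**What to change.** In SAP 7.8.4:

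1. Delete the sentence that makes log(conc) conditional on non-normal concentrations, and state that raw concentration is the model scale.
2. Add an explicit linearity check, since none is specified now: for example, residuals against concentration, or AIC of the alternative against the linear model.
3. Allow log(conc) or another shape only if that check shows departure, with a stated rule for the zero placebo concentrations and a matching ESTIMATE contrast.
4. Always report the raw-concentration model beside any alternative.
5. State whether predictions are made at the first-dose C_max, at C_max,ss, or at both.

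The cost is a few sentences of SAP wording and a little extra output. No new data are needed.
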